6.3 Follow-up Telephone Call (Day 2)

A study clinician or trained research assistant will contact the participant via telephone the following day to assess safety.

6.4 Optional follow up procedure:

Participants may undergo a second session of imaging and study drug administration following approximately 8 weeks of exposure to antipsychotic medication. They will receive the same study drug (placebo, low dose levetiracetam or higher dose levetiracetam) that they received at their first session. This follow-up imaging may provide important information about possible changes in brain activation following medication compared to healthy controls and whether levetiracetam is likely to benefit individuals when added to antipsychotic medication. If subjects elect to remain medication-free, after a delay of at least 2 weeks they may return for a second session of imaging and administration of levetiracetam or placebo. They will also receive the same study drug (placebo, low dose levetiracetam or higher dose levetiracetam) that they received at their first session. This will provide important information about whether hippocampal ASL changes with severity of psychosis and whether the effect of levetiracetam on hippocampal ASL changes with severity of psychosis. Individuals will receive the same remuneration for all three sessions (initial session, session following initiation of antipsychotic medication and session following a progression of psychotic symptom severity off-medication). Thus, participants are not incentivized to remain medication free—they will have an opportunity to repeat the procedure regardless of their decision about medication.

The follow-up procedure will include the following assessments:

1. Medical history, including patient demographics, and any concomitant medications use (including over-the-counter medications, vitamins, and supplements) will be reviewed and recorded.

CONFIDENTIAL

This material is the property of the NYU School of Medicine and Langone Medical Center. Do not disclose or use except as authorized in writing by the study sponsor

2. Physical examination will be completed by study MD or nurse practitioner. Vital signs will also be completed by a trained study team member.
3. A urine pregnancy test will be performed on all females of childbearing potential.
4. A urine drug screen test will be performed.
5. In addition, the following rating scales will be completed:
 - a. Columbia Suicide Severity Rating Scale (CSSR-S)
6. Subsequently, participants will complete the imaging section of the visit, which will include all procedures outlined above under Baseline (Visit 2 – Day 1)

7 Statistical Plan

7.1 Sample Size Determination

We are not testing for statistical significance and are not powering the study based on estimates of statistical significance. This is a pilot study to determine whether we have an adequate signal to proceed to a fully-powered clinical trial (R33). In keeping with the NIMH “fast fail” guidelines, we are selecting a threshold which will provide reasonable evidence to support continuing to the next phase of development. The decision to proceed to the R33 trial will be based on the demonstration of target engagement, defined by an effect size (Cohen’s d) of .5 or greater in the mean reduction by levetiracetam of hippocampal perfusion measured by ASL compared to placebo, plus the demonstration of adequate tolerability defined by the absence of serious adverse events and confirmed by review of safety and tolerability data with the DSMB and NIMH staff. The decision whether to proceed and the selection of the optimal dose will be made in conjunction with NIMH staff.

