In the study of hippocampal CBF measured by ASL in UHR and EP subjects by Allen and colleagues (12), the elevation in left hippocampal CBF compared to healthy controls was a very large effect (Z statistic = 4.35). In addition, repeated measurements of hippocampal CBF in subjects who remained psychotic were highly reliable (12). Bakker and colleagues (58) found that levetiracetam decreased elevated hippocampal activation in patients with MCI to levels below those observed in healthy controls (from 0.8 to -0.2 in MCI patients vs. 0.0 in healthy controls). The magnitude of reduction of hippocampal hyperactivation with levetiracetam was highly consistent between trials involving two patient samples (58). Furthermore, the method of ASL that we will use to measure hippocampal CBF has very high reliability (ICC=0.90) (51). Therefore, based on previous studies, the elevation of hippocampal activation in our sample should be large, the reduction by levetiracetam should also be large, and our method for measurement is highly reliable, so we are confident that our proposed approach for verifying target engagement is quite valid and feasible. In addition, two hours post-dose should be sufficient to measure levetiracetam effects with ASL since maximal blood levels are achieved within one hour and, within one hour of oral levetiracetam administration, abolition of seizures has been demonstrated in humans with photosensitive epilepsy {Kastelein-Nolst Trenite, 1996 #6357} and within one hour a reduction of corticospinal excitability measured by transcranial magnetic stimulation (TMS) has been demonstrated in healthy human subjects {Kastelein-Nolst Trenite, 1996 #6357}. Because a single dose can treat epilepsy within the two hour time frame of our R61 study and because perfusion as measured by

CONFIDENTIAL

This material is the property of the NYU School of Medicine and Langone Medical Center. Do not disclose or use except as authorized in writing by the study sponsor

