We will use the signal difference in healthy white matter (WM) as reference. This approach, justified by animal evidence, exploits the fact that cerebral blood flow (CBF) is ~3x lower in WM compared to gray matter (GM). Deviations from this assumption introduce a relatively minor bias on cerebral GM flow (51). Our measurements of the resting cortical CBF agree with CBF measured using O¹⁵ PET. However, the precision of our technique is double that of competing methods (51), likely due to the use of WM as reference. The tissue perfusion computation uses a general kinetic model (61). WM and GM segmentation is done directly from bSSFP images. To avoid blood vessel contamination, we use only cortical voxels with CBF values < 150 mL/(100 g min). Although this will exclude only the largest blood vessels, smaller vessels likely do not contribute to the “through flow” artifact (51).

In a two-week trial, levetiracetam doses of 62.5 mg bid and 125 mg bid reduced hippocampal activation and improved cognition in a sample of MCI patients with a mean age of 70 years whereas a dose of 250 mg bid was not effective {Bakker, 2015 #6213}. Due to an estimated 30% reduction in renal clearance in the elderly {Contin, #6359}, these effective doses would be equivalent to 84 mg bid and 167 mg bid in young EP patients. We selected an intermediate value of 125 mg bid (half-way between 84 mg and 167 mg); a single dose of 185 mg is calculated to produce blood levels equivalent to blood levels achieved at steady state following repeated dosing of 125 mg bid. Therefore, we will administer a single levetiracetam dose of 185 mg to achieve blood levels within the range of steady state blood levels that were effective in elderly patients with MCI. The 500 mg levetiracetam dose is a standard antiepileptic dose for partial (temporal

CONFIDENTIAL

This material is the property of the NYU School of Medicine and Langone Medical Center. Do not disclose or use except as authorized in writing by the study sponsor

lobe) epilepsy. We expect that both doses of levetiracetam will be well-tolerated; in the treatment of epilepsy, levetiracetam doses up to 3 g are routinely administered without serious side effects.

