It is possible that a low dose of levetiracetam “optimizes” synaptic transmission and is preferable to a higher antiepileptic dose in MCI, but we cannot be certain that this will also hold true for first episode psychosis. We thus selected two doses: a dose that achieves blood levels within the range that was effective for MCI (correcting for age and calculating a single dose that will produce blood levels equivalent to steady state concentrations achieved by repeated dosing) and a typical anticonvulsant dose for which we can be confident of full target engagement. Since it is a trade-off between the number of doses examined and the sample size in each dose group, we believe it is better to perform a definitive test of these two doses than to risk having an under-powered test of multiple doses.

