3.2 Primary Study Endpoints

The primary efficacy outcome measure for the R61 clinical trial is the change from baseline in hippocampal CBF measured by ASL; the Go/NoGo signal will be based on the effect size magnitude rather than formal hypothesis testing.

CONFIDENTIAL

This material is the property of the NYU School of Medicine and Langone Medical Center. Do not disclose or use except as authorized in writing by the study sponsor

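### Does the Go criterion in Section 7.1 need a named SD and a two-dose rule before it can be used?

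*Combined protocol and SAP*

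**What the plan says.** Section 3.2 makes change from baseline in hippocampal CBF by ASL the primary efficacy outcome and adds that "the Go/NoGo signal will be based on the effect size magnitude rather than formal hypothesis testing". Section 7.1 disclaims power and significance testing and continues: "This is a pilot study to determine whether we have an adequate signal to proceed to a fully-powered clinical trial (R33"). "The decision to proceed to the R33 trial will be based on the demonstration of target engagement", and engagement means a Cohen's d "of .5 or greater in the mean reduction by levetiracetam of hippocampal perfusion measured by ASL compared to placebo". Go also requires that no serious adverse event occurs and that the DSMB and NIMH staff review safety and tolerability. Both the decision to proceed and the choice of dose are taken jointly with NIMH staff.

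The trial has three randomized arms: placebo, 185 mg and 500 mg, allocated 1:1:1 (5.2, 5.3). The Study Summary sets a minimum of 8 eligible completers per arm, and 5.2 caps randomization at 46. Section 7.2 analyses everyone who receives study drug.

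Section 1.4 defends the choice of two doses by saying that "it is better to perform a definitive test of these two doses than to risk having an under-powered test of multiple doses".

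**The concern.** Two features look wrong on first reading.

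First, the only numeric rule in the plan can be computed in more than one way. Cohen's d needs an SD, and 7.1 names none: it could be the SD of change or the baseline SD. There are also two active arms and one threshold. Either dose might be enough, both might be required, or the two might be pooled against placebo. The case in which this matters most is one the protocol raises itself. In MCI two lower doses worked, "whereas a dose of 250 mg bid was not effective", and 1.4 says a low dose possibly "is preferable to a higher antiepileptic dose in MCI, but we cannot be certain that this will also hold true" in first-episode psychosis. If only one dose works, the three rules can give different answers. A reading chosen after the data are seen would leave the decision to start an 84-subject R33 trial open to the result.

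Second, a test called definitive in 1.4 is described in 7.1 as a pilot without power. Neither section gives the chance that an inert drug passes.

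**Working it through.** The plan states no power, alpha or false-Go rate, so there is no figure to reproduce beyond 3 × 8 = 24, which agrees with the minimum in 5.2.

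**Inputs.** Threshold d = 0.5 (7.1); n = 8 per arm as a minimum (Study Summary); at most 46 randomized (5.2), and 46/3 = 15.3, so about 15 per arm; one shared placebo arm.

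**Inert drug, SD-of-change scaling.** For two arms of size n, t = d × √(n/2) on 2n − 2 df.

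- n = 8: t = 0.5 × √4 = 1.0 on 14 df; upper tail 0.167.
- n = 15: t = 0.5 × √7.5 = 1.369 on 28 df; upper tail 0.091.
- Doses pooled, 16 against 8: t = 0.5 × √(16 × 8/24) = 1.155 on 22 df; upper tail 0.130.

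The either-dose and both-dose rules share a placebo arm, so they were simulated.

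| True d (one dose, other dose), n = 8 | Either | Pooled | Both |
|---|---|---|---|
| 0, 0 | 26.7% | 13.0% | 6.7% |
| 0.5, 0 | 53.9% | 28.0% | 13.4% |
| 0.5, 0.5 | 67.4% | 50.5% | 34.0% |

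In the middle row the either and both rules disagree in 40.5% of trials, and either and pooled in 26.0%. At 15 per arm an inert drug passes on either dose 15.3% of the time.

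**Inert drug, baseline-SD scaling.** Here SD(change)/SD(baseline) = √(2(1 − r)), where r is the pre/post correlation. With n = 8, the per-dose rate (either-dose in brackets) is 20.6% (32.2%) at r = 0.3, 16.7% (26.7%) at 0.5, 10.9% (18.2%) at 0.7, 6.9% (11.8%) at 0.8 and 2.1% (3.9%) at 0.9. The documents do not give r over two hours in these patients. Section 1.4 says only that "the method of ASL that we will use to measure hippocampal CBF has very high reliability (ICC=0.90"), which is a property of the method, so r is an assumption and the range is shown.

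**Which reading the text supports.**

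- *SD.* The outcome in 3.2 is a change score, and 7.1 compares mean reductions between groups. The ordinary Cohen's d for a between-group difference in a change score divides by the pooled SD of that change.
- *Doses.* The Study Summary says the trial is to find a dose that works and then select one for R33. The last sentence of 7.1 refers to choosing the best dose. Section 1.4 reserves its fallback, a repeat with two weeks of dosing, for the case where neither dose lowers perfusion. A pooled d cannot rank doses, and requiring both to pass sits badly with choosing one. Comparing each dose with placebo, with one pass sufficient, is what fits.

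**Two figures that seem to strengthen the concern but do not.**

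- A dose with true d = 0.5 is missed 49.3% of the time at n = 8. The truth then lies on the cut-off, so the rate stays near one half at any size: 49.5% at n = 15 and 49.8% at n = 100. It says nothing about this design. At true d = 0.8 the miss rate is 27.2% at n = 8.
- For an inert drug that passes on either dose, the larger d averages 0.83. For a single dose with no choosing, the mean of d given d ≥ 0.5 is already 0.81. Almost all the inflation comes from passing a threshold, and about 0.02 from picking the larger dose.

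**The case for a change.** The strongest case for a change is that the rule decides whether R33 starts, that a numeric screen should be computable in only one way, and that a few sentences fixed before analysis would cost no patients and leave the threshold alone. If the either-dose reading is intended, the relevant inert-drug rate is about 27%, and it appears nowhere in the plan. Joint judgement with NIMH staff does not define d. An observed d of 0.5 at 8 per arm has a 95% CI from −0.51 to 1.49, which is far from definitive.

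Much of this stands as fact: 7.1 names neither the SD nor the two-dose rule, and the arithmetic is right. What does not stand is the inference that the plan yields a wrong result. The wide spread of rates comes from setting the reading that fits the text against ones that fit it less well. The rates at 8 per arm treat a minimum as the analysed size, although recruitment continues until the slowest arm reaches 8 and 7.2 includes everyone dosed. The one-active-dose case is also only one of the protocol's expectations: 1.4 is confident that the anticonvulsant dose engages the target fully. Nothing in the documents suggests that the reading would be chosen after the data are seen.

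**Conclusion.** No change to the plan follows. The missing SD and two-dose rule are a definition left unwritten. Analysts working from 3.2, the Study Summary and 7.1 would use the pooled SD of change and compare each dose with placebo, with one dose at 0.5 or more meeting the criterion. On that reading an inert drug meets it 16.7% of the time per dose and 26.7% for either dose at the minimum of 8 per arm, falling to 9.1% and about 15% at 15 per arm. The other Go conditions can only lower these rates. For a fast-fail pilot that says openly it is neither powered nor tested, that is a fair trade-off. Printing the rates would alter neither the threshold nor the data, nor who takes the decision.

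The word definitive in 1.4 is loose. It compares two doses with a larger number of doses, carries no figure, and is overridden by the plain disclaimer in 7.1.

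The figures assume normally distributed changes with equal variance across arms and equal arm sizes. The conclusion also rests on the either-dose, SD-of-change reading being the intended one, which the text implies but does not state.

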7.2 Subject Population(s) for Analysis

Both the incidence of adverse effects and ASL evidence of hippocampal target engagement will be analyzed in all participants who receive study drug. The primary efficacy outcome measure for this trial are described above in section 3.2.

8 Safety and Adverse Events

8.1 Definitions

Unanticipated Problems Involving Risk to Subjects or Others

Any incident, experience, or outcome that meets all of the following criteria:

- Unexpected in nature, severity, or frequency (i.e. not described in study-related documents such as the IRB-approved protocol or consent form, the investigators brochure, etc.)
- Related or possibly related to participation in the research (i.e. possibly related means there is a reasonable possibility that the incident experience, or outcome may have been caused by the procedures involved in the research)

CONFIDENTIAL

This material is the property of the NYU School of Medicine and Langone Medical Center. Do not disclose or use except as authorized in writing by the study sponsor

- Suggests that the research places subjects or others at greater risk of harm (including physical, psychological, economic, or social harm).

Adverse Event

An **adverse event** (AE) is any symptom, sign, illness or experience that develops or worsens in severity during the course of the study. Intercurrent illnesses or injuries should be regarded as adverse events. Abnormal results of diagnostic procedures are considered to be adverse events if the abnormality:

- results in study withdrawal
- is associated with a serious adverse event
- is associated with clinical signs or symptoms
- leads to additional treatment or to further diagnostic tests
- is considered by the investigator to be of clinical significance

Serious Adverse Event

Adverse events are classified as serious or non-serious. A **serious adverse event** is any AE that is:

- fatal
- life-threatening
- requires or prolongs hospital stay
- results in persistent or significant disability or incapacity
- a congenital anomaly or birth defect
- an important medical event

Important medical events are those that may not be immediately life threatening, but are clearly of major clinical significance. They may jeopardize the subject, and may require intervention to prevent one of the other serious outcomes noted above. For example, drug overdose or abuse, a seizure that did not result in in-patient hospitalization or intensive treatment of bronchospasm in an emergency department would typically be considered serious.

All adverse events that do not meet any of the criteria for serious should be regarded as **non-serious adverse events**.

Adverse Event Reporting Period

The study period during which adverse events must be reported is normally defined as the period from the initiation of any study procedures to the end of the study treatment follow-up. For this study, the study treatment follow-up is defined as 30 days following the last administration of study treatment.

Preexisting Condition

A preexisting condition is one that is present at the start of the study. A preexisting condition should be recorded as an adverse event if the frequency, intensity, or the character of the condition worsens during the study period.

CONFIDENTIAL

This material is the property of the NYU School of Medicine and Langone Medical Center. Do not disclose or use except as authorized in writing by the study sponsor

General Physical Examination Findings

At screening, any clinically significant abnormality should be recorded as a preexisting condition. At the end of the study, any new clinically significant findings/abnormalities that meet the definition of an adverse event must also be recorded and documented as an adverse event.

Post-study Adverse Event

All unresolved adverse events should be followed by the investigator until the events are resolved, the subject is lost to follow-up, or the adverse event is otherwise explained. At the last scheduled visit, the investigator should instruct each subject to report any subsequent event(s) that the subject, or the subject's personal physician, believes might reasonably be related to participation in this study. The investigator should notify the study sponsor of any death or adverse event occurring at any time after a subject has discontinued or terminated study participation that may reasonably be related to this study. The sponsor should also be notified if the investigator should become aware of the development of cancer or of a congenital anomaly in a subsequently conceived offspring of a subject that has participated in this study.

Abnormal Laboratory Values

A clinical laboratory abnormality should be documented as an adverse event if any one of the following conditions is met:

- The laboratory abnormality is not otherwise refuted by a repeat test to confirm the abnormality
- The abnormality suggests a disease and/or organ toxicity
- The abnormality is of a degree that requires active management; e.g. change of dose, discontinuation of the drug, more frequent follow-up assessments, further diagnostic investigation, etc.

Hospitalization, Prolonged Hospitalization or Surgery

Any adverse event that results in hospitalization or prolonged hospitalization should be documented and reported as a serious adverse event unless specifically instructed otherwise in this protocol. Any condition responsible for surgery should be documented as an adverse event if the condition meets the criteria for an adverse event.

Neither the condition, hospitalization, prolonged hospitalization, nor surgery are reported as an adverse event in the following circumstances:

- Hospitalization or prolonged hospitalization for diagnostic or elective surgical procedures for a preexisting condition. Surgery should **not** be reported as an outcome of an adverse event if the purpose of the surgery was elective or diagnostic and the outcome was uneventful.
- Hospitalization or prolonged hospitalization required to allow efficacy measurement for the study.
- Hospitalization or prolonged hospitalization for therapy of the target disease of the study, unless it is a worsening or increase in frequency of hospital admissions as judged by the clinical investigator.

CONFIDENTIAL

This material is the property of the NYU School of Medicine and Langone Medical Center. Do not disclose or use except as authorized in writing by the study sponsor

Procedures to minimize additional risks:

As described, a psychiatrist will provide a psychiatric and medical evaluation as part of screening. A study MD or nurse practitioner will be present at the imaging center during the procedure and will evaluate the participant after completion of the scanning procedure to affirm that the participant is safe to leave after completing the study. Subjects will also be contacted by telephone the following day to affirm that they are stable. We will follow the same emergency procedures that are followed at the imaging center in the event of adverse reactions to contrast agents or other medical complications—the study physician ([name] or [name]) will respond to the event along with other CBI staff (including a nurse) and 911 will be called if needed. We are studying a low dose and an extremely low dose of levetiracetam. The low dose is the standard starting dose which has been approved for almost 20 years and is not associated with medical complications.

Psychiatric reactions occur but usually only after 1 week of daily dosing—we will be monitoring closely for psychiatric reactions to the single dose, even though this is highly unlikely to occur.

